## PHQ-9- Patient Health Questionnaire

Subject ID: \_\_\_\_\_ Date (dd/mmm/yyyy): \_\_\_\_/\_\_\_\_/\_\_\_\_

Over the last 2 weeks, how often have you been bothered by any of the following problems?  
(use "✓" to indicate your answer)

	Not at all	Several days	More than half the days	Nearly every day
1. Little interest or pleasure in doing things	0	1	2	3
2. Feeling down, depressed, or hopeless	0	1	2	3
3. Trouble falling or staying asleep, or sleeping too much	0	1	2	3
4. Feeling tired or having little energy	0	1	2	3
5. Poor appetite or overeating	0	1	2	3
6. Feeling bad about yourself—or that you are a failure or have let yourself or your family down	0	1	2	3
7. Trouble concentrating on things, such as reading the newspaper or watching television	0	1	2	3
8. Moving or speaking so slowly that other people could have noticed. Or the opposite — being so fidgety or restless that you have been moving around a lot more than usual	0	1	2	3
9. Thoughts that you would be better off dead, or of hurting yourself	0	1	2	3

add columns  +  +

(Healthcare professional: For interpretation of TOTAL, please refer to accompanying scoring card). TOTAL:

10. If you checked off any problems, how difficult have these problems made it for you to do your work, take care of things at home, or get along with other people?	Not difficult at all _____ Somewhat difficult _____ Very difficult _____ Extremely difficult _____
---	---

**PROMIS Item Bank v1.0 - Sleep Disturbance - Short Form 4a**

Subject ID: \_\_\_\_\_

Date (dd/mmm/yyyy): \_\_\_\_/\_\_\_\_/\_\_\_\_

In the past 7 days...		Very poor	Poor	Fair	Good	Very good
1	My sleep quality was .....					
In the past 7 days...		Not at all	A little bit	Somewhat	Quite a bit	Very much
2	My sleep was refreshing. ....					
3	I had a problem with my sleep.....					
4	I had difficulty falling asleep .....					

## PATIENTS' GLOBAL IMPRESSION OF CHANGE (PGIC) SCALE

Subject ID: \_\_\_\_\_

Date (dd/mmm/yyyy): \_\_\_\_/\_\_\_\_/\_\_\_\_

Chief Complaint (Presenting Problem): \_\_\_\_\_

Since beginning treatment at this clinic, how would you describe the change (if any) in ACTIVITY LIMITATIONS, SYMPTOMS, EMOTIONS, and OVERALL QUALITY OF LIFE, related to your painful condition? Please circle the number below, that matches your degree of change since beginning care at this clinic for the above stated chief complaint.

No change	Almost the same	A little better	Somewhat better	Moderately better	Better	A great deal better
1	2	3	4	5	6	7

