### 3.2 Exclusion Criteria

- Participants with a Pacemaker
- Participants with irregular heart rate or a heart rate lower than 60 beats per minute (bradycardia)
- Have had a transplant within the last 2 years
- Have had a heart attack or cardiac bypass surgery within the last 12 months
- History of substance abuse, including prescription drugs, within the last 12 months
- Patients with complaints of dizziness or lightheadedness within the last 3 months
- Women who are pregnant

- Participants with Diabetic Retinopathy
- Current Ear infection
- SBP < 100 and/or DBP < 60
- History of uncontrolled bipolar disorder within the last 12 months
- History of uncontrolled seizures within the last 12 months
- History of Aneurysms
- History of syncope within the last 12 months
- Participants that have had a TIA or stroke within the last 12 months
- Participants with health problems deemed at risk for the study by the Principal Investigator
- Participants with any changes to Pain/Anxiety/Depression/Sleeplessness medications within last 60 days (participants that do not meet this medication-change washout period may be delayed until 60-day period is met)
- Participants that are currently under adjudication process for disability support, VA or other

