- Participants should be able to perform their typical day-to-day activities while wearing the device. They may shower while wearing the Nu-V3 device, provided that they do not get the device wet and use the small disposable ear covers that are provided for them.
- Patients should not change their existing forms of treatment or medications without discussion with the investigator.
- Nu-Life reserves the right to capture video, photographs and written testimonials from patients with written permission. In the event subjects elect to participate in any or all of these activities, they will be asked to sign a waiver giving exclusive rights to Nu-Life for the materials gathered from the patient, such as video, photographs and written testimonials. Their participation in this study is not dependent upon their willingness to provide these testimonial materials.

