## 8.0 STUDY ENDPOINT and DATA ANALYSIS

### 8.1 Primary Endpoints: Primary endpoints consisted of the following:

Safety: The primary safety endpoint is the occurrence of reported unanticipated problems involving risk to subjects or others (“UPIRTSOs”). These UPIRTSOs are defined as those problems which alter the risks to subjects or others. This includes any study suspensions or holds. The primary safety endpoint analyses will be based on a risk-benefit conclusion.

Effectiveness: The primary effectiveness endpoints are an overall change in median reported symptoms of pain, anxiety, depression, and/or sleeplessness via numeric rating scales at 8 weeks. This primary effectiveness is measured by median reported symptom changes in pain, anxiety, depression, and/or sleeplessness for respective stratified populations via the following validated tools: Pain - Pain Intensity and Interference (PEG\_Scale), Anxiety - Generalized Anxiety Disorder 7-item (GAD-7) scale, Depression - Patient Health Questionnaire (PHQ-9), Sleeplessness - PROMIS short form 4a, and overall improvement of quality of life (QOL) - Patient’s Global Impression of Change (PGIC).

The hypothesis-driven criterion of effectiveness is to show that there is a statistically significant reduction in the median reported pain, anxiety, depression, and/or sleeplessness levels of patients using the Nu-V3 device. The second criterion is intended to show that there is a statistically significant improvement in reported quality of life and perceived treatment benefit, secondary to overall reported symptom reductions of pain, anxiety, depression, and/or sleeplessness.

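### The PGIC, a primary effectiveness tool, asks about change since care began at the clinic rather than since Nu-V3 was first worn, so established patients' scores can mix pre-study change with change on the device

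*Protocol*

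**What the plan says.** The time anchor appears twice on the PGIC form in Protocol Appendix 11. The question begins "Since beginning treatment at this clinic, how would you describe the change (if any". The answer instruction asks for the number "that matches your degree of change since beginning care at this clinic for the above stated chief complaint". Neither sentence mentions Nu-V3, the study or the first visit.

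Protocol 8.1 lists "overall improvement of quality of life (QOL) - Patient’s Global Impression of Change (PGIC" among the five tools that measure primary effectiveness at 8 weeks, and the SAP's Primary Endpoints text does the same. In both documents a second criterion calls for a statistically significant gain in reported quality of life. The SAP presents the study as the main support for the De Novo request.

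The assessment tables (Protocol 4.1 and SAP) mark the PGIC row at Weeks 2 to 8 and Week 12, with no mark at Week 1. Protocol 4.0 describes a single-arm, open-label study of 50-100 patients.

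Protocol 3.1, 3.2 and the Appendix 4 checklist contain nothing that keeps out a site's existing patients. Two passages show that participants may arrive already under treatment: "Patients should not change their existing forms of treatment or medications without discussion with the investigator" (4.0) and the exclusion of "Participants with any changes to Pain/Anxiety/Depression/Sleeplessness medications within last 60 days" (3.2).

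**The concern.** A global impression of change is defined by its starting point. Here that point is when care began at the clinic. For a participant whose first treatment there is Nu-V3, this coincides with the start of the device period. For one already treated at the site for the same complaint, it lies further back, and the rating covers both periods. The same score then means different things in different participants.

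At stake is the second primary criterion, on quality of life. A single-arm study has no comparison group in which the same pre-study change would appear and cancel. Protocol 5.0 plans to compare questionnaires completed before the device with later ones, but the PGIC row provides no pre-device rating for that comparison.

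**Working it through.** The documents give no test, null value, alpha or expected PGIC result, so there is no stated figure to reproduce. The check is mainly a comparison of texts.

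**1. Recall periods of the five primary tools (Appendix 11).**
- PEG: past week.
- PROMIS Sleep Disturbance 4a: past 7 days.
- GAD-7 and PHQ-9: last 2 weeks.
- PGIC: from the start of treatment or care at the clinic, with no fixed length.

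Only the PGIC has an open-ended starting point. In the same packet, item 1 of the PTB-7 asks about benefit from Nu-V3 by name, so device-specific wording was available.

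**2. Who is affected.** Only participants treated before Week 1 at the same site and for the same chief complaint. The eligibility criteria allow them; no passage says how many there are.

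**3. Direction.** For an established participant, let A be the period before Week 1 and B the period on the device. The form asks about A plus B; the endpoint needs B.
- Better in A, unchanged in B: the form records improvement, and the device is over-credited.
- Worse in A, better in B by the same amount: the form records no net change, and device benefit is hidden.
- Better in A, worse in B: the form may still record improvement, and deterioration on the device is hidden.
- Unchanged in A: form and endpoint agree.

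The error can therefore run either way. With a wholly inert device it can only raise scores, because the lowest score (1) covers both no change and worsening.

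**4. Illustrative size.** Assume an inert device. Let f be the share of participants already in the site's care for the complaint, and q the share of those who would score 5-7 because of that care. The 5-7 cut comes from the provider note on the form. Spurious favourable share = f × q; count = N × f × q. All values of f and q are assumptions.
- f = 0.10, q = 0.30: 0.10 × 0.30 = 3%, or 1.5 of 50 and 3 of 100.
- f = 0.30, q = 0.50: 0.30 × 0.50 = 15%, or 7.5 of 50 and 15 of 100.
- f = 0.50, q = 0.60: 0.50 × 0.60 = 30%, or 15 of 50 and 30 of 100.
- f = 0.70, q = 0.50: 0.70 × 0.50 = 35%, or 17.5 of 50 and 35 of 100.

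**5. What this would do to the endpoint.** The plan speaks of medians, not a 5-7 responder rate. If everyone else scored 1, even 35% of participants at 5-7 would leave the median at 1, since 35% is below half. A test against 1 is more sensitive. Suppose a sign test were used (the plan names none). Nobody can score below 1, so six scores above 1 give a two-sided p of 2 × 0.5^6 = 0.031, while five give 2 × 0.5^5 = 0.0625. Six is 12% of 50 or 6% of 100. The chance of at least six is:
- at a 3% spurious share: 0.4% for N = 50 and 8.1% for N = 100;
- at 15%: 78% and 99.8%;
- at 30%: above 99% for both.

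This sensitivity comes partly from the scale's floor, not from the anchor alone.

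**The case against.** **The exposed group is not shown to exist.** The medication rule and the sentence on existing treatment show care somewhere, not at the study site. For someone treated elsewhere, the clinic anchor coincides with the start of Nu-V3. This stands. A reader might infer that established site patients are expected; the documents only fail to exclude them.

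**The bias need not favour the device.** A reader might infer a one-way inflation. Participants enter with symptoms, and the SAP calls those symptoms uncontrolled, so earlier decline is plausible and could mask benefit. This stands.

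**Some correction is possible.** The PGIC is repeated weekly from Week 2 to Week 8, and the provider note mentions a two-point change from the last score. A Week 2 to Week 8 comparison would remove much of a stable pre-study component. It would also discard the device effect already present at Week 2, and no such analysis is planned. So it would be too strong to say the pre-study part can never be separated, but the remedy is only partial.

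**Context may guide the reader.** Protocol 5.0 and the PTB-7 instructions use treatment to mean Nu-V3, and some participants will read the PGIC question that way. The answer instruction, with "matches your degree of change since beginning care at this clinic", is harder to read so. The process maps and consent pages are not available here, so clarifying site instructions cannot be ruled out.

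**A Week 1 rating might exist.** Protocol 4.0 mentions quality of life at baseline, and the footnote to the general ePRO row names the PGIC. The PGIC's own row nevertheless starts at Week 2.

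**Conclusion.** The point holds as a defect in the printed question. The PGIC asks about the wrong period for any participant already treated at the site for the same complaint, and nothing visible in either document resets the anchor. The consequence is conditional: the score can credit the device with earlier improvement or conceal its benefit, and how often depends on an unstated number of established patients.

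The range of roughly 3-35% spurious favourable scores shows scale only. It rests on an inert device, assumed f and q, and a 5-7 cut that the plan does not adopt as its endpoint. It is not an estimate for this trial.

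A reader might also conclude that primary effectiveness as a whole is compromised. The documents do not support that: PEG, GAD-7, PHQ-9 and PROMIS 4a have fixed recall and do not share the problem. The exposure is confined to the quality-of-life part of primary effectiveness and the same measure among the secondary endpoints. The phrase "related to your painful condition" in the same question raises a separate issue of scope, not of timing. The anchor should be corrected, since doing so is cheap and the instrument is primary.

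**What to change.** In the Appendix 11 PGIC, replace both anchors with first Nu-V3 placement, identified as the Week 1 visit. Add a short justification, because Protocol 8.1 describes the tool as validated. Check that the Provider and Family versions, whose text is not visible here, use the same anchor.

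Record for each participant whether the site was treating the complaint before Week 1. State in the SAP that the PGIC will be reported separately for new and established patients. This matters most for data already collected with the present wording.

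The cost is a change to one ePRO screen with IRB notification, one extra baseline item and a written justification. Scores from before and after the rewording are not interchangeable, and the PGIC result may change.

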## 3.0 STUDY PARTICIPANT SELECTION CRITERIA

### 3.1 Inclusion Criteria

- Participant is at least 18 years of age
- Participant presents with one or more of the following symptoms: pain, depression, anxiety, and/or sleeplessness
- Participant is capable of understanding the use and maintenance of the device
- Participant is capable and agreeing to participate in the ongoing assessment
- Participant has signed the Informed Consent Form
- Participant can commit to follow all protocol study timepoints

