## 4.0 STUDY PROTOCOL

The Nu-V3 Clinical Study is a prospective, single-arm, open-label, multi-center study using the Nu-V3 cranial nerve stimulation treatment device in patients with pain, anxiety, depression, and/or sleeplessness.

For this Phase I study, a total of 50-100 patients at multiple centers will be registered for study participation. Study participants are those who have signed the informed consent form, met the inclusion and exclusion criteria, and are enrolled in the study at one of multiple sites. Enrolled participants are stratified based on their pain, anxiety, depression, and/or sleeplessness symptom presentation at baseline and treated with the Nu-V3 device for 8 weeks, then observed for an additional 4 weeks. Interim analysis of reported data will be based on baseline stratifications and conducted at 4, 8, and 12 weeks during this time. Post study, participants will be given the chance to continue with an optional maintenance treatment with the Nu-V3 device per a 2-weeks on, 2-weeks off schedule, for an additional 12 weeks, with an 8-week observation.

Subjects enrolled onto the Nu-V3 Clinical Trial will undergo the following regimen:

- At the baseline visit, patients will be asked to complete study questionnaires (Appendix 11) regarding all of the following symptoms: pain, anxiety, depression, and/or sleeplessness, as well as their quality of life, active medications, medical history, and demographical information.
- At each subsequent visit, patients will be asked to complete study questionnaires regarding all the following symptoms: pain, anxiety, depression, and/or sleeplessness, as well as their activity level and quality of life.
- The sessions will begin with the Nu-V3 device being placed on the left ear and three small pads (non-invasive) being placed on the ear. Each Nu-V3 device

lasts for up to 14 days with a change in the pads approximately 7 days into the treatment.

- Each session takes approximately 15-20 minutes. The placement of the device takes approximately 5 minutes and the remaining time is spent verifying ePRO form completion, and evaluating the patient for all device effects.
- The Nu-V3 device is mobile and is worn externally on the left ear 24 hours a day during treatment, fitting comfortably behind the ear. An electrical signal is sent to the external ear through coated wire leads attached to the device and adhesive pads which attach to three sites on the ear.

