#### 4.1 Phase I Study Assessment Tables

Nu-Life Solutions Miniaturized Wearable Medical Technology - Nu-V3		Study Treatment Assessments Table										Nu-V3
		*Evaluations are completed weekly, every 7 days =3 days										
Evaluation*	Study Treatment											
	Week 1	Week 2	Week 3	Week 4	Week 5	Week 6	Week 7	Week 8	Week 9-11	Week 12		
Informed Consent	x											
Inclusion and Exclusion 	x											
Patient Registration 	x											
Medications Form 	x			x				x		x		
Patient Onboarding and Orientation 	x											
In office assessment	x	x	x	x	x	x	x	x		x		
New Device Placed	x		x		x		x					
Pad Replaced		x		x		x		x				
Treatment Forms 	x	x	x	x	x	x	x	x				
No Device									x	x		
ePRO Questionnaires 	x	x	x	x	x	x	x	x	x	x		
Patients' Global Impression of Change ePRO form (PGIC) 		x	x	x	x	x	x	x		x		
Providers' Global Impression of Change ePRO form (PGIC)		x	x	x	x	x	x	x		x		
Family Global Impression of Change ePRO form (PGIC)		x	x	x	x	x	x	x		x		
Optional Patient Media Testimony	x			x				x		x		

1. Inclusion/Exclusion, Registration, Medications, Treatment forms to be completed by site coordinator via online module.  
 2. Patient Onboarding and Orientation includes introductory demographics form, Nu-V3 patient training video  
 3. ePRO questionnaires completed on patient's mobile device: DQ-9 (baseline), PTB-7, PEG, GAD-7, PHQ-9, PROMIS 4a, PGIC  
 4. If patient consents to media testimony, site will collect via study collection process every 4 weeks.

Evaluation*	Post Study Intervention Assessments Table														
	*Evaluations are completed weekly, every 7 days ±3 days														
	Optional Maintenance Therapy										Long Term Follow Up				
Week 13	Week 14	Week 15-16	Week 17	Week 18	Week 19-20	Week 21	Week 22	Week 23	Week 24	Week 25	Week 26	Week 27-28	Week 29	Weeks 30-31	Week 32
Medications Form 				x			x			x					x
In office assessment	x	x		x	x		x	x							
New Device Placed	x			x			x								
Pad Replaced		x			x			x							
Treatment Forms 	x	x		x	x		x	x							
No Device			x			x			x	x	x	x	x	x	x
ePRO Questionnaires 	x	x		x	x		x	x	x	x		x			x
Patients' Global Impression of Change ePRO form (PGIC) 	x	x		x	x		x	x				X			X
Providers' Global Impression of Change ePRO form (PGIC)		x			x			x				X			X
Family Global Impression of Change ePRO form (PGIC)		x			x			x				X			X
Optional Patient Media Testimony		x			x			x				x			X

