1. Inclusion/Exclusion, Registration, Medications, Treatment forms to be completed by site coordinator via online module.
2. Patient Onboarding and Orientation includes introductory demographics form, Nu-V3 patient training video
3. ePRO questionnaires completed on patient's mobile device: DQ-9 (baseline), PTB-7, PEG, GAD-7, PHQ-9, PROMIS 4a, PGIC
4. If patient consents to media testimony, site will collect via study collection process every 4 weeks.

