- Nu-Life reserves the right to capture video, photographs and written testimonials from patients with written permission. In the event subjects elect to participate in any or all of these activities, they will be asked to sign a waiver giving exclusive rights to the video, photographs and written testimonials captured to Nu-Life. Their participation in this study is not dependent upon their willingness to participate in video, photographs or written testimonials.

 Study Treatment Assessments Table 										
*Evaluations are completed weekly, every 7 days ≈3 days										
Evaluation*	Study Treatment									
	Week 1	Week 2	Week 3	Week 4	Week 5	Week 6	Week 7	Week 8	Week 9-11	Week 12
Informed Consent	x									
Inclusion and Exclusion ¹	x									
Patient Registration ¹	x									
Medications Form ¹	x			x				x		x
Patient Onboarding and Orientation ²	x									
In office assessment	x	x	x	x	x	x	x	x		x
New Device Placed	x		x		x		x			
Pad Replaced		x		x		x		x		
Treatment Forms ¹	x	x	x	x	x	x	x	x		
No Device									x	x
ePRO Questionnaires ³	x	x	x	x	x	x	x	x	x	x
Patients' Global Impression of Change ePRO form (PGIC) ³		x	x	x	x	x	x	x		x
Providers' Global Impression of Change ePRO form (PGIC)		x	x	x	x	x	x	x		x
Family Global Impression of Change ePRO form (PGIC)		x	x	x	x	x	x	x		x
Optional Patient Media Testimony	x			x				x		x

1. Inclusion/Exclusion, Registration, Medications, Treatment forms to be completed by site coordinator via online module.
2. Patient Onboarding and Orientation includes introductory demographics form, Nu-V3 patient training video
3. ePRO questionnaires completed on patient's mobile device: DQ-9 (baseline), PTB-7, PEG, GAD-7, PHQ-9, PROMIS 4a, PGIC
4. If patient consents to media testimony, site will collect via study collection process every 4 weeks.

Study Endpoints and Data Analysis: The study endpoints data were collected from each participant's study questionnaires. The data were collected electronically via the patient's own device, and were uploaded to an electronic data capture system. The data were used to demonstrate that the Nu-V3 device provides participants with relief of the symptoms of pain, depression, anxiety and/or sleeplessness. The data analysis includes comparative data for each participant's questionnaire prior to beginning treatment with the Nu-V3 device, the participant's weekly questionnaires during treatment and the questionnaire completed at the end of the treatment with the Nu-V3 device.

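### No readable text fixes the PGIC's chief complaint before treatment, so the target of a primary Week 8 measure may be named or changed once the response is known

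*Protocol*

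**What the plan says.** - **Role.** Protocol 8.1 and the SAP's Primary Endpoints list the PGIC, as the measure of overall quality of life, among the primary effectiveness tools at Week 8. Both also use it at Weeks 4, 8 and 12 as a secondary measure.
- **What is rated.** The form in Protocol Appendix 11 has a line labelled "Chief Complaint (Presenting Problem" and left blank. It then asks for the "degree of change since beginning care at this clinic for the above stated chief complaint". The same item also contains the words "related to your painful condition".
- **Who completes it.** The notes to the tables in Protocol 4.1 read: "ePRO questionnaires completed on patient's mobile device: DQ-9 (baseline), PTB-7, PEG, GAD-7, PHQ-9, PROMIS 4a, PGIC". The form ends with a patient signature line.
- **When.** The row "Patients' Global Impression of Change ePRO form (PGIC" in the Study Treatment Assessments Table (SAP, and the same table in Protocol 4.1) has no mark at Week 1. It is marked at Weeks 2 to 8 and at Week 12. The row "New Device Placed" is first marked at Week 1.
- **Who enters.** Protocol 3.1: "Participant presents with one or more of the following symptoms: pain, depression, anxiety, and/or sleeplessness".
- **What is fixed at baseline.** Protocol 4.0: "Enrolled participants are stratified based on their pain, anxiety, depression, and/or sleeplessness symptom presentation at baseline". This can give one patient several symptoms. It does not designate a chief complaint.

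**The concern.** A change rating needs a fixed target. Here the target is whatever stands on the complaint line. If that line is first filled after a week of treatment and left open on each later form, a patient with several presenting symptoms can rate the one that has improved.

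Two things are at stake. First, the trial is single-arm and open-label. No control group would show the same selection, so any such choice passes straight into the estimated benefit. Second, ratings from one patient at Weeks 4, 8 and 12 may refer to different complaints. They could not then be read as a course over time, and the form's note to the provider, which treats a 2-point change from the last score as significant, would lose its meaning.

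**Working it through.** The documents give no expected PGIC rate, sample-size calculation or significance level for this measure, so there is no planned figure to reproduce. The check is mainly of the text.

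**1. Timing.** First device placement: Week 1. First mark in the PGIC row: Week 2. Forms due in the 12-week study by that row: 7 (Weeks 2 to 8) + 1 (Week 12) = 8. The general ePRO row is marked at Week 1 and at Weeks 9–11 as well, and its footnote lists the PGIC. The two rows therefore disagree. The dedicated row is the more specific, and a rating of change has no meaning before treatment, so I read the first PGIC as Week 2 and the count as 8.

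**2. Is one complaint recorded before treatment?** None of these readable forms has a chief-complaint field: eligibility checklist (Appendix 4), medical history (Appendix 8), weekly treatment form (Appendix 9), demographics (Appendix 11). Three items could hold one but cannot be read here: the online registration form, the baseline process map (Appendix 3, a figure) and the medications form (Appendix 10).

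**3. Is it carried forward?** No readable text says that the line is pre-filled, locked or repeated from visit to visit. Protocol 5.0 limits the symptom-response analysis to the stratified indication(s), which may be several, so it does not fix the complaint. The SAP's Quality of Life–PGIC template is blank on the point.

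**4. Illustration of an upper bound (all inputs assumed).** Let *p* be the chance that one complaint, fixed in advance, is rated 5–7, which the form calls favourable. Let every patient have *k* symptoms and name the one that improved most. If symptoms are independent,

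P(rated 5–7) = 1 − (1 − *p*)^*k*.

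With *p* = 0.20: *k* = 2 gives 1 − 0.80² = 0.36; *k* = 4 gives 1 − 0.80⁴ = 1 − 0.41 = 0.59.

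For correlated symptoms I used *k* standard normal scores with common correlation, counted a patient as favourable if the largest exceeded the 1 − *p* quantile, and simulated 1,000,000 draws:

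| *p* | *k* | independent | correlation 0.5 | correlation 0.8 |
|---|---|---|---|---|
| 0.10 | 2 | 0.19 | 0.17 | 0.14 |
| 0.10 | 4 | 0.34 | 0.26 | 0.19 |
| 0.20 | 2 | 0.36 | 0.31 | 0.27 |
| 0.20 | 4 | 0.59 | 0.44 | 0.34 |
| 0.30 | 2 | 0.51 | 0.44 | 0.39 |
| 0.30 | 4 | 0.76 | 0.59 | 0.47 |

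A patient with one symptom, or one who rates a complaint settled without regard to outcome, contributes *p* and no bias.

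**The case against.** The case on the other side has real force.

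- **The label is an anchor.** Presenting problem, together with a rating counted from the start of care, points to what the patient came in with. This stands as the intended meaning. But for a patient who presents with several symptoms each is a presenting problem, and nothing readable makes the patient choose one before treatment.
- **The form does not say who fills the line.** That it is the patient is an inference from the form being a patient ePRO. The appendix prints a paper-style form for an electronic instrument, so a printed blank does not show how the electronic field behaves. This stands.
- **A baseline record may exist in material that cannot be read here.** This also stands, and the point is limited accordingly.
- **The item is global.** It asks for one judgement across activity, symptoms, emotions and quality of life, and the plan uses it for overall quality of life. A best-of-*k* model treats it as *k* separate symptom scores. It also counts 5–7 ratings, whereas the plan speaks of medians and the 5–7 cut appears only in a note to the provider. That is a fair limit on the figures. It does not remove the point, because the instruction for circling the number ties the rating to the stated complaint.

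A reader might infer that patients are shown to write in a new complaint at each visit and pick the one that improved, or that the PGIC is inflated by the amounts in the table. The documents support neither. They leave the possibility open, and they hold no data on how the line is used.

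**Conclusion.** The point holds as a gap in specification. A primary Week 8 measure is rated against a complaint that no readable text fixes before treatment or keeps constant afterwards. A patient with several presenting symptoms may name or change it after the response is known.

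The size of any bias cannot be derived from the documents. The tabulated values are upper bounds for their assumed rate, number of symptoms and correlation, and hold only if every patient names the most improved symptom.

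The conclusion rests on three readings: the dedicated PGIC row governs rather than the footnote to the ePRO row; the patient fills the line; and the unreadable baseline material holds no locked complaint. If the electronic form already carries forward a complaint recorded before placement, a sentence saying so would close the point. I would class this as a change that should be made because it is cheap, not as a flaw that invalidates the trial.

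**What to change.** 1. At Week 1, before the device is placed, record the presenting problem, chosen from the patient's stratified symptom(s).
2. Pre-fill it, read-only, on every later PGIC.
3. State in Protocol 8.1 and in the SAP's Primary Endpoints that the Week 8 PGIC refers to that complaint. Align the ePRO footnote with the PGIC row, so that it is clear that no PGIC is due at Week 1.
4. For forms already collected, list the patients whose written complaint changes across their own forms or lies outside their baseline stratum. Report a sensitivity analysis without those patients. Comparing with the stratum alone is not enough, because a patient stratified to all four symptoms could switch among them and never be flagged. State two limits: the exclusion uses entries made after treatment began, and the check cannot detect a complaint chosen after the response and then repeated on every form.

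**Cost.** One extra field at Week 1, one pre-filled field in the ePRO and a sentence in each document, with no added visit or questionnaire. The PGIC result may be less favourable.
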